4.2 Inclusion in the Intervention arm

If a participant is allocated to the intervention arm, they receive the IY-I Book. Following the first follow up (2 months post baseline), only participants with a Parent PHQ-9 score ≥ 5 OR Child ASQ:SE2 score \geq 'Monitoring' in the intervention arm are offered the IY-I programme. Following the second follow up (9 months post baseline) only participants with Parent PHQ-9

³ In protocol v10 the CARE Index is described as a child attachment measure and listed as a child secondary outcome. Child attachment is just one part of the Index and we will use the overall dyadic synchrony score which is a parent-child dyad measure.

score ≥ 5 OR Child ASQ:SE2 score \geq 'Monitoring' in the intervention arm are offered the IY-T programme.

Non-research participants may be included in the IY-I and IY-T groups. Parents can be invited by service staff to join the group based on professional judgement/assessment that they meet the same eligibility criteria as research participants. We do not collect data for these participants; they attend as they would for any other parenting intervention delivered at that site. This is accepted practice in these types of research interventions when there are concerns about group size.

4.3 Blinding

The trial statistician will remain blind during the study until database freeze. At database freeze, the statistician will receive unblinded data. Full details of blinding can be found in the study protocol (v10).

5 Interim Analysis & Study Monitoring

The following committees have been established:

1. **Trial Steering Committee (TSC)** - consists of an independent chair, a member with early years expertise, an independent statistician, lay representatives (including a member of the Parent Advisory Committee) and the chief investigator. The role of the TSC is to provide supervision of the protocol and statistical analysis plan, to provide advice on and monitor progress of the study, to review information from other sources and consider recommendations from the DMEC. The TSC will meet at regular intervals as outlined in the TSC terms of reference. The TSC can prematurely close the trial following advice from the sponsor, funder, DMEC or TMG.
2. **Trial Management Group (TMG)** – The TMG consists of the chief investigator, trial managers and others as deemed necessary. The CI chairs the meetings at regular intervals as agreed by the group and oversees the day to day implementation of the trial in accordance with the terms of reference.
3. **Data Monitoring and Ethics Committee (DMEC)**- includes an independent chair and two independent members. The DMEC works in accordance with an agreed Charter, reviewing reports provided by the CTRU to assess the progress of the study, the safety data and the critical endpoint data as required.

These committees function in accordance with Sheffield CTRU standard operating procedures. Membership details of these committees are provided in the protocol (v10).

6 Data Collection

6.1 Data Sources

The randomisation list is held on the CTRU's randomisation system. Trial data are extracted from source documents and entered onto the CTRU's in house data management system (PROSPECT). University of York staff conduct a data entry check on a 10% sample of CRFs. The data management team in the Sheffield CTRU validate and query electronic data for inconsistencies during the course of the trial (as stipulated in SOP DM005), The trial statistician will conduct any additional validation checks where appropriate before database lock (as guided by ST003, DM005 and DM012). Details of data collected at each time point are given in Table 1.

Table 1: List of outcome measures and timing of data collection

Outcome measures	Baseline	2 month follow up (FU1)	9 month follow up (FU2)	18 month follow up (FU3)
Primary care-giver				
PHQ-9	X	X	X	X
PSoC	X	X	X	X
EQ5D-5L	X	X	X	X
MPAS/PPAS				X
CSRI	X	X	X	X
Child				
ASQ:SE-2	X	X	X	X
PEDSQL				X
SDQ				X
CSRI	X	X	X	X
Co-parent				
PHQ-9	X	X	X	X
PSoC	X	X	X	X
EQ5D-5L	X	X	X	X
CSRI	X	X	X	X
Parent-child dyads				
CARE Index	X	X	X	X

7 Statistical Analysis

7.1 General Considerations

Data will be reported according to the Consolidated Standards Of Reporting Trials (CONSORT) statement for individually randomised parallel group trials (Schulz, Altman and Moher, 2010) and extension (Juszczak *et al.*, 2019).

Summaries of continuous variables will comprise the number of observations used, mean, median, standard deviation (SD), inter-quartile range (IQR), minimum and maximum as appropriate for the distribution of the data.

Summaries of categorical variables will comprise the number of observations used, and the number and percentage of observations in each category. Tables containing the results of the statistical modelling will present the overall difference between treatment groups with two-sided 95% confidence intervals (CI) and p-values. Hypothesis tests will use a two-sided 5% significance level.

Complete details of data derivations and methods for handling missing data is covered in sections 8.1 and 9.

All analyses are based on the overall score only unless otherwise stated.

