2.2 Secondary outcome measures

2.2.1 Child secondary outcome measures¹

The following measures are completed independently by parent and co-parent at all three timepoints unless otherwise stated.

- a) Behaviour – measured at 18-month follow-up using parent/co-parent report *Strengths and Difficulties Questionnaire (SDQ)*.
- b) Cognitive development – measured at 18-month follow-up using parent/co-parent report *PedsQL Infant Scale*.
- c) Health (quality of life) – measured at 18-month follow-up using parent/co-parent report *PedsQL Infant Scale*.
- d) Service use – using parent report: *Client Service Receipt Inventory (CSRI)*.

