7.8 Analysis of other secondary outcomes

Not all secondary outcomes will be collected at all four time points. For those outcomes that have been collected at all four time points (PSoC, EQ5D-5L, CARE Index), mean scores by treatment arm will be presented in line plots (Figure 4) and the impact of the intervention on these outcomes will be investigated using the same approach as the primary analysis of the primary outcome.

For those outcomes only collected at FU3 (MPAS/PPAS, PEDSQL, SDQ), descriptive statistics will be presented by treatment arm. A multiple linear regression model will be used to estimate the adjusted mean difference between treatment arms. Stratification variables (baseline PHQ-9 score, baseline ASQ:SE-2 score, sex of child and site) will be included in the model as covariates.

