8.1.2 Missing items within questionnaires

The scoring of questionnaires with missing items is described in table 2 for the primary outcome (ASQ:SE-2), key secondary outcome (PHQ-9) and SDQ. Justification for the approach taken is also provided in the table.

For other secondary outcomes appropriate guidance does not exist so we will impute up to 25% missing values using the average score of completed items for surveys / time-points where more than 5% of responses have item non-response. Where questions are subdivided into groups this rule will be applied at the group level. Where there are no groupings of survey questions this rule will be applied at the whole survey level.

9 Data manipulations and definitions

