9.2 Patient reported outcomes

Table 2: Summary questionnaires and how the scores are calculated

Name	Score range	Description	Interpretation of score
Primary caregiver and co-parent			
PHQ-9	0-27	Measure of depression. 9 item questionnaire, 0-3 for each item	
 - Score 1-04 = minimal depression - Score 5-09 = mild depression - Score 10-14 = moderate depression - Score 15-19 = moderately severe depression - Score 20-27 = severe depression 
Desired direction of effect: decrease
 
Imputation: up to 2 missing values will be imputed using the average score for completed items based on NHS guidance (NHS, no date)

PSoC	0-100	The PSoC contains 17 items developed to assess parenting self-esteem. The measure has two subscales, related to parent satisfaction (e.g., A difficult problem in being a parent is not knowing whether you're doing a good job or a bad one), and	
Scores 70 to 96 = high parental confidence
 
Scores 51 to 69 = moderate parental confidence

		parent self-efficacy (e.g., Being a parent is manageable, and any problems are easily solved). Items are rated on a 6-point scale ranging from strongly agree (1) to strongly disagree (6)	Scores 16 to 50 = low parental confidence Desired direction of effect: increase
EQ-5D-5L	This section of the questionnaire yields a total of 243 theoretically possible health states.	The measure comprises 6 questions. The main EQ-5D-5L health utility is based on questions 1-5 (mobility, self-care, usual activities, pain/discomfort, and anxiety/depression), each of which are scored on a five point scale (1: best response, 5: worst). The final question is a stand-alone item, a 0-10 self-assessed thermometer scale scored in units of 0.1 (0=worst, 10=best).	0 = equivalent to death 1 = full health negative score = state worse than death Desired direction of effect: increase

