MPAS	Quality of attachment: Minimum score = 9, Maximum score = 45. Absence of Hostility: Minimum score = 5, Maximum score = 25. Pleasure in interaction: Minimum	The MPAS contains 19 items developed to assess a mother's attachment to their infant during the first year of life. Each item is scored on a 2, 3, 4, or 5 point scale. Items are scored on different scales: 
 - Items 8 and 12 are scored on a 2-point scale - Item 14 is scored on a 3-point scale - Items 4, 5, 6, 7, 10, 15, 16, 17, 18 and 19 are scored on a 4-point scale - Items 1, 2, 3, 9, 11 and 13 are scored on a 5-point scale. To ensure equal weighting of all questions it is recommended that responses should be recoded to represent a score of 1 (low attachment) to 5 (high attachment) for every question: 
 - Item 1 would be scored as 1; 2; 3; 4; 5 - Item 2 would be scored as 1; 2; 3; 4; 5 	
 - Quality of attachment: Low scores indicate poor quality of attachment - Absence of Hostility: Low scores indicate high levels of hostility. - Pleasure in interaction: Low scores indicate a lack of pleasure in interaction. Desired direction of effect: increase

	
score = 5, Maximum score = 25.
	
 - Item 3 would be scored as 1; 2; 3; 4; 5 - Item 4 would be scored as: 1; 2.3; 3.6; 5 - Item 5 would be scored as 1; 2.3; 3.6; 5 - Item 6 would be scored as 1; 2.3; 3.6; 5 - Item 7 would be (reverse) scored as: 5; 3.6; 2.3; 1 - Item 8 would be (reverse) scored as: 5; 1 - Item 9 would be (reverse) scored as: 5; 4; 3; 2; 1 - Item 10 would be (reverse) scored as: 5; 3.6; 2.3; 1 - Item 11 would be (reverse) scored as: 5; 4; 3; 2; 1 - Item 12 would be (reverse) scored as: 5; 1 - Item 13 would be (reverse) scored as: 5; 4; 3; 2; 1 - Item 14 would be (reverse) scored as: 5; 3; 1 - Item 15 would be scored as 1; 2.3; 3.6; 5 - Item 16 would be scored as 1; 2.3; 3.6; 5 - Item 17 would be scored as 1; 2.3; 3.6; 5 - Item 18 would be scored as 1; 2.3; 3.6; 5 - Item 19 would be scored as 1; 2.3; 3.6; 5 
The 19 items can be pooled together to create three factors for analysis (with items in brackets reverse scored):
 
 - Quality of attachment: items 3 4 5 6 (7) (10) (14) 18 19 - Absence of hostility: items 1 2 15 16 17 - Pleasure in interaction: all items reversed (8 9 11 12 13) 	

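### Two secondary-outcome scoring rules fail when followed: cognitive development gets no analysis of its own, and item-mean imputation can give EQ-5D-5L levels that have no utility

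*SAP*

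**What the plan says.** **PedsQL.** Section 2.2.1 lists two child outcomes, (b) "Cognitive development – measured at 18-month follow-up using parent/co-parent report" and (c) "Health (quality of life) – measured at 18-month follow-up using parent/co-parent report", and assigns both to the PedsQL Infant Scale. Section 7.1 sets the default: "All analyses are based on the overall score only unless otherwise stated". Section 7.8 then says: "For those outcomes only collected at FU3 (MPAS/PPAS, PEDSQL, SDQ), descriptive statistics will be presented by treatment arm", followed by a multiple linear regression for the adjusted mean difference. PedsQL appears there once. Table 2 in section 9.2 names cognitive functioning among five dimensions, but gives formulas only for the psychosocial, physical and total scores.

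**EQ-5D-5L.** Section 8.1.2 gives separate missing-item rules for ASQ:SE-2, PHQ-9 and SDQ. For all other secondary outcomes, "we will impute up to 25% missing values using the average score of completed items", at surveys or time-points where more than 5% of responses have item non-response. The rule works within groups of questions where these exist, and otherwise on the whole survey. EQ-5D-5L is not exempted. Table 2 bases the utility on five questions with five levels each, adds a 0-10 thermometer, and states: "This section of the questionnaire yields a total of 243 theoretically possible health states". Section 7.8 models EQ-5D-5L by the same approach as the primary outcome.

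**The concern.** Section 7.1 refers the reader to sections 8.1 and 9 for the complete derivations, so these are the rules a statistician would program.

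On PedsQL, the program would produce one total score and one treatment effect. An outcome that the plan lists in its own right would have no estimate, unless someone later decided to add a subscale.

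On EQ-5D-5L, the utility is defined for health states made of whole levels. A mean of other dimensions is usually not a whole level, so the index could not be calculated without an unplanned step such as rounding or interpolation.

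Under sections 4.3 and 11 the statistician receives unblinded data at database freeze. Choices left open here could therefore be made with allocation known.

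**Working it through.** **1. PedsQL (no arithmetic; the sections side by side)**

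- Section 2.2.1: two outcomes, one instrument.
- Section 7.1: overall score only, unless stated otherwise.
- Section 7.8: PedsQL as a single entry; no subscale named.
- Table 2: the total runs over all scales. The psychosocial summary pools the emotional, social and cognitive items. No separate cognitive score is defined for analysis.

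The cognitive items therefore contribute to the total and to the psychosocial summary, and no section plans a model for cognitive development itself. Elsewhere the plan does name the score it will use: the total difficulties score for SDQ (Table 2) and dyadic synchrony for the CARE Index (section 9.3).

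**2. EQ-5D-5L imputation**

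Inputs: five dimensions at levels 1 to 5 (Table 2); a 25% limit and a more-than-5% trigger (section 8.1.2).

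- One missing dimension: 1/5 = 20%, or 1/6 = 17% if the thermometer counts as a sixth item. Both are within 25%.
- Two missing: 2/5 = 40%, or 2/6 = 33%. Both exceed 25%, so only the one-missing case arises.
- Patterns of four completed dimensions: 5^4 = 625.
- The mean is a whole level only if the sum is 4, 8, 12, 16 or 20. The counts are 1 + 35 + 85 + 35 + 1 = 157.
- Not a whole level: 625 − 157 = 468, and 468/625 = 74.9% of patterns.
- Examples: levels 1, 1, 1, 2 give 5/4 = 1.25; levels 1, 1, 2, 3 give 7/4 = 1.75. Neither is an EQ-5D-5L level.
- If the thermometer counts as a completed item, levels 1, 1, 1, 2 with a reading of 8.0 give (5 + 8.0)/5 = 2.6. That mean mixes scales that run in opposite directions.

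**3. Smaller errors in Table 2**

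- Health states: the stated 243 equals 3^5. Five items at five levels give 5^5 = 3,125.
- PSoC: the stated range is 0-100. With 17 items scored 1 to 6 it is 17 × 1 = 17 to 17 × 6 = 102. The bands run from 16 to 96, which is 16 × 1 to 16 × 6. With 17 items a score of 16 cannot occur, and 97 to 102 fall in no band.
- PSoC direction: "Items are rated on a 6-point scale ranging from" strongly agree (1) to strongly disagree (6). Agreement is unfavourable for one of the two example items and favourable for the other, but no reversed items are listed. MPAS and PPAS reversals are listed item by item.

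**The case against.** **PedsQL.** Section 7.1 allows exceptions. Listing cognitive development in section 2.2.1, with Table 2 naming the dimension and giving a 0-100 subscale range, could be read as one. This is a weak reading, because neither section 7.8 nor Table 2 says that the subscale is analysed. It does show that the repair is one line. A reader might also infer that the same total will be tested twice under two names. The text does not support that: section 7.8 lists PedsQL once, and no second model is planned.

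**EQ-5D-5L.** The rule is conditional. It applies only above the 5% trigger, and whole-number means remain valid in form (1, 1, 1, 1 gives 1). The SAP gives no expected item non-response, so the number of participants affected cannot be estimated. This limits the size of the point but does not remove the fault in the rule.

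**MPAS/PPAS.** A reader might infer that these scales also go unanalysed, since Table 2 gives them no overall score. Table 2 does state otherwise: "The 19 items can be pooled together to create three factors for analysis".

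**PSoC.** A reader might infer that items will be totalled without reversal, so that the score loses its meaning. The plan does not say so. The desired direction is an increase, and bands from 16 to 96 describe low to high confidence across their whole span only if all items run the same way. The reversals are unlisted detail. The bands enter no planned model, and the figure of 243 feeds no calculation.

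**Conclusion.** Two rules go wrong when followed as written, both on secondary outcomes.

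- Cognitive development, a listed child outcome, has no analysis of its own. This follows from sections 2.2.1, 7.1, 7.8 and Table 2 read together, and needs no assumption beyond taking the section 7.1 default at its word.
- Where more than 5% of responses at a time-point have item non-response, an EQ-5D-5L form with one missing dimension can be given a level that belongs to none of the 3,125 states. This happens for 468 of 625 patterns. The figure treats the five dimensions as the group to which the rule applies, and says nothing about how common each pattern is among participants.

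It would go too far to say that the utilities of all partial responders are invalid: the trigger may not be met, and some means are whole levels. The state count and the PSoC range, bands and reversals are real corrections to Table 2, but nothing in the plan shows that they would change an estimate.

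**What to change.** 1. In section 7.8 and Table 2, name the PedsQL cognitive functioning subscale as the analysed score for outcome (b) and the PedsQL total for outcome (c). The cost is one additional secondary estimate.
2. In section 8.1.2, exempt EQ-5D-5L from the 25% item-mean rule. Treat the utility as missing if any dimension is missing, and handle that missing value at index level. The cost is that a few partial responses become missing.
3. In Table 2, replace 243 with 3,125, bring the PSoC range and bands into line with the number of items used, and list the reverse-scored PSoC items. The cost is wording only.

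All three should be settled before database freeze, when the statistician is unblinded.

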7.2 Participant flow

A CONSORT style flow diagram will show the flow of participants through the trial (Figure 1). In addition to the flow diagram, tables showing more detailed summaries of the reasons for refused consent and reasons for withdrawal will be presented.

7.2.1 Attrition

There are several reasons that a participant may not complete outcome data collection. These include withdrawal of consent and loss to follow up. The number and proportion in each category will be presented by intervention arm.

The number of each type of discontinuation will be presented as part of the CONSORT flow diagram and will be summarised in more detail in a separate table which will include the timing of discontinuation (between randomisation & FU1, between FU1 & FU2, between FU2 & FU3) where possible (Appendix, Table 4). Where given, the reasons for withdrawal of consent will be presented.

7.3 Baseline Characteristics

The baseline demographics and clinical characteristics of the participants will be reported. For the continuous variables (e.g. age) mean and SD, median and IQR and minimum and maximum values will be presented. The number of observations used in each calculation will be presented alongside the summaries. For the categorical variables, (e.g. ethnicity), the number and percentage of participants in each of the categories and the total number of observations will be presented.

All baseline summaries will be presented and reported for each treatment group and in total. No statistical significance testing will be done to test baseline imbalances between the intervention arms but any noteworthy differences will be descriptively reported.

The following summaries will be presented:

Demographics

- Child: Age (weeks), Sex, Ethnicity
- Primary caregiver: Age, Sex, Ethnicity, Religion, Income, Marital Status, Highest qualification previously achieved
- Co-parent: Age, Sex, Ethnicity, Religion, Income, Marital Status, Highest qualification previously achieved

Outcome measures

-
- Child: ASQ:SE-2,
 - Primary caregiver: PHQ-9, PSoC, EQ5D-5L
 - Co-parent: PHQ-9, PSoC, EQ5D-5L
 - Parent-child dyad – CARE Index

Other measures

- Child: Premature, Difficulties at birth, Received immunisation
- Parent-child dyad – details of child feeding methods

Baseline summaries will be presented separately by child, primary caregiver and co-parent (Appendix Table 4, Table 5).

7.4 Intervention Adherence & Fidelity

The number and proportion of participants who received the book will be presented. For the IY-I and IY-T stages, the following intervention attendance summaries (Appendix Table 11) will be presented:

- Number offered/eligible for IY-I or IY-T at each site
- Number of groups at each site
- Session size for each group by week
- Session size (median, IQR, minimum, maximum)
- Number of sessions attended per participant (median, IQR, minimum, maximum)
- The proportion of participants attending at least 1/2/3/5/10/12 sessions (denominator to be all those who attended at least 1 session)

Methods for the assessment of fidelity will be part of the Process Evaluation component of the study which is described in further detail in the study protocol v10.

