7.5.2 Per protocol

The per-protocol analysis will be descriptive because there is no satisfactory way to define a per-protocol population for those in receipt of IY-B only. If the per-protocol population definition were based on IY-I and IY-T only we would only be removing people with higher scores at follow up 2 and 3 which would reduce the effects size compared to the ITT analysis and bias upwards the estimated impact on compliers because efficacy is demonstrated by a reduction in primary outcome.

Instead we will undertake a descriptive analysis comparing the characteristics of compliers compared to non-compliers. For example did compliers tend to be people with the greatest need (scores just over the eligibility threshold) or those with the higher scores. The characteristics investigated in this descriptive analysis will be the same as those used for the subgroups. This descriptive analysis will be an important input to the process evaluation.

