10.1 Subgroup analyses

As suggested by the literature, the subgroup analysis will be restricted to the primary analysis and subgroups will be defined by baseline data i.e. data that is not dependent on the intervention. The subgroup analysis will be performed using the primary analysis of the primary outcome model (ASQ:SE-2). An interaction statistical test between the randomised treatment group and subgroup will be used to directly examine the strength of evidence for the difference between treatment arms varying between subgroups. Subgroup analysis will be performed regardless of the results of the primary analysis. The mean difference and 95% CI will be computed for each subgroup category and visually displayed using a forest plot. The regression coefficient for the interaction between treatment group and subgroup will be presented with the associated confidence interval and P-value. We will not calculate separate p-values within each subgroup category (Wang et al. 2007). Results will be presented as shown in Appendix Table 9. The subgroups of interest are described below.

- **Social and economic background** using a binary variable for whether or not the primary caregiver was educated to degree level as a proxy. In a previous US study

(Lavigne *et al.*, 2008) mothers educated to high school level or below (typically left education aged 17 or 18) responded better to parent training than better educated mothers. Participants with overseas and vocational qualifications will be allocated to the higher education group if they left full time education aged 19 or above.

- **First child (Yes or No).** A Netherlands study found that intervention mothers of first-born children displayed an increase in their use of positive discipline strategies as compared to first-time mothers in the control group. (Stolk *et al.*, 2008)
- **Sex of index child (Male or Female)** child gender has been found to differentiate response in previous trials of parenting interventions (Lavigne *et al.*, 2008); (Gardner *et al.*, 2010).
- **Site**

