	xx	xx.x(xx.x)	xx	xx.x(xx.x)	xx	xx.x(xx.x-xx.x)	0.xxxx
	xx	xx.x(xx.x)	xx	xx.x(xx.x)	xx	xx.x(xx.x-xx.x)	
	xx	xx.x(xx.x)	xx	xx.x(xx.x)	xx	xx.x(xx.x-xx.x)	
	xx	xx.x(xx.x)	xx	xx.x(xx.x)	xx	xx.x(xx.x-xx.x)	0.xxxx

* p-value from interaction test

vi. Safety analysis results

Table 10: Summary of safety data

	Intervention	Control	All
Number (%) of participants who experienced ≥ 1 AE	xx(xx.x%)	xx(xx.x%)	xx(xx.x%)
Number of all AEs (including repeated events)	xx	xx	xx
AE related to intervention			
Unlikely	xx(xx.x%)	xx(xx.x%)	xx(xx.x%)
Unrelated	xx(xx.x%)	xx(xx.x%)	xx(xx.x%)
	Intervention	Control	All
Number (%) of participants who experienced ≥ 1 SAE	xx(xx.x%)	xx(xx.x%)	xx(xx.x%)
Number of all SAEs (including repeated events)	xx	xx	xx
SAE related to intervention			
Unrelated	xx(xx.x%)	xx(xx.x%)	xx(xx.x%)
Intensity of SAE			
Mild	xx(xx.x%)	xx(xx.x%)	xx(xx.x%)
Moderate	xx(xx.x%)	xx(xx.x%)	xx(xx.x%)
Severe	xx(xx.x%)	xx(xx.x%)	xx(xx.x%)
Frequency of SAE			
Isolated	xx(xx.x%)	xx(xx.x%)	xx(xx.x%)
Intermittent	xx(xx.x%)	xx(xx.x%)	xx(xx.x%)
Unknown	xx(xx.x%)	xx(xx.x%)	xx(xx.x%)

vii. Adherence to intervention

Table 11: Summary of the number of sessions received by participants

Programme	Consent			Number of sessions						
				1	2	3	5	8**	10	12
IY-I	Xx	Attended at least this many sessions	n	xx	xx	xx	xx	xx	xx	xx
			(%)	xx%	xx%	xx%	xx%	xx%	xx%	xx%
IY-T	xx	Attended at least this many sessions	n	xx	xx	xx	xx	xx	xx	xx
			(%)	xx%	xx%	xx%	xx%	xx%	xx%	xx%

Table 12: Summary of IY-I and IY-T groups

	Number assigned to a group	Number who attended one or more sessions	Median sessions attended (IQR)	Min, Max.
IY-I	xx	xx(xx%)	xx(xx,xx)	x,xx
IY-T	xx	xx(xx%)	xx(xx,xx)	x,xx

Table 13: Summary of all intervention sessions

	Number of Sessions that occurred	Median (IQR)	Min, Max.
IY-I	xx	xx(xx,xx)	x,xx
IY-T	xx	xx(xx,xx)	x,xx

Table 14: Summary of breastfeeding at baseline

Variable		Intervention	Control	All
		(n=xxx)	(n=xxx)	(n=xxx)
Breastfeeding History	Never breastfed	xx(xx.x%)	xx(xx.x%)	xx(xx.x%)
	Previously breastfed, now stopped	xx(xx.x%)	xx(xx.x%)	xx(xx.x%)
	Currently breastfeeding -	xx(xx.x%)	xx(xx.x%)	xx(xx.x%)
	Not Known ¹	xx(xx.x%)	xx(xx.x%)	xx(xx.x%)
Of those currently breastfeeding	Does not use bottle	xx(xx.x%)	xx(xx.x%)	xx(xx.x%)
	Also uses bottle	xx(xx.x%)	xx(xx.x%)	xx(xx.x%)
Childs age when stopped breastfeeding (weeks)	N (%)	xx(xx.x%)	xx(xx.x%)	xx(xx.x%)
	Mean (SD)	xx.x (xx.x)	xx.x (xx.x)	xx.x (xx.x)
	Median (IQR)	xx.x(xx,xx)	xx.x(xx,xx)	xx.x(xx,xx)

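### The complier comparison in SAP 7.5.2 contains no score and so cannot answer its own question, and the session percentages in 7.4 describe retention among attenders, with no percentage of all those offered planned.

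*SAP*

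**What the plan says.** **Complier comparison.** Section 7.5.2 rejects a per-protocol population and plans a description of compliers against non-compliers, as an input to the process evaluation. Its example question is "did compliers tend to be people with the greatest need (scores just over the eligibility threshold) or those with the higher scores". The variables are then fixed: "The characteristics investigated in this descriptive analysis will be the same as those used for the subgroups". Section 10.1 states that "subgroups will be defined by baseline data i.e. data that is not dependent on the intervention" and lists four subgroups:

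- social and economic background, measured by "whether or not the primary caregiver was educated to degree level as a proxy";
- first child;
- sex of the index child;
- site.

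**Attendance.** Section 7.4 lists several summaries for the two group programmes. One is "Number offered/eligible for IY-I or IY-T at each site". Another is "The proportion of participants attending at least 1/2/3/5/10/12 sessions", with "denominator to be all those who attended at least 1 session". Appendix A Table 11 shows n and % at each session threshold, next to a column headed Consent. Appendix A Table 12 has a column "Number who attended one or more sessions", as n (%), beside the count assigned to a group.

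**The concern.** Both summaries are meant to show how the stepped programmes were taken up, and each is fixed in a way that works against that purpose.

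In 7.5.2 the question is about where compliers' scores lay relative to the eligibility threshold, yet no score is among the variables compared. The parenthesis in the question also attaches the greatest need to the wrong end of the eligible range, which could reverse the interpretation of any result.

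In 7.4 a family that was offered a group and never came is the clearest case of non-adherence, and the stated denominator leaves that family out.

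The stake is interpretive. Section 7.5.2 reduces the per-protocol analysis to description and section 7.6.2 rules out a CACE analysis. If the ITT result is null, these summaries are the main material within this SAP for judging whether eligible families received the group programmes.

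**Working it through.** **1. Can the comparison in 7.5.2 answer its question?**

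- Scores needed: section 4.2 sets eligibility by PHQ-9 of 5 or more, or ASQ:SE-2 at or above Monitoring. These are assessed at FU1 for IY-I and at FU2 for IY-T.
- Variables supplied: education, first child, sex of child, site (section 10.1).
- Overlap: none. No PHQ-9 or ASQ:SE-2 score is listed for any visit. The FU1 and FU2 scores are also excluded by rule, because 10.1 confines subgroups to baseline data.

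The comparison as fixed cannot separate compliers just over the threshold from those well above it.

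**2. Which end of the range is the greatest need?**

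- PHQ-9 (Table 2): 5–9 is mild, rising to 20–27 severe; a decrease is desired.
- ASQ:SE-2 (Table 2): on the 6-month version 30–44 is Monitor and 45+ is Refer; on the 12-month version 40–49 and 50+; a decrease is desired.

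Just over the threshold is therefore the least need among eligible families. The label in 7.5.2 is reversed.

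**3. What do the percentages in 7.4 measure?**

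The SAP states no uptake or attendance figure, so there is nothing to reproduce. Let E be the number offered, A the number attending at least one session, N_k the number attending at least k sessions, u = A/E the uptake, and q = N_k/A.

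- Percentage under the stated rule: N_k/A = q.
- Percentage of those offered: N_k/E = (N_k/A) × (A/E) = q × u.
- Ratio of the first to the second: q/(q × u) = 1/u.
- For k = 1, N_1 = A, so the stated rule gives A/A = 100% whatever the uptake.

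Neither u nor q is in the document. The table assumes q = 60% for some threshold and a range for u.

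| Assumed uptake u | At least 1 session: stated rule | At least 1 session: of those offered | Threshold with q = 60%: stated rule | Threshold with q = 60%: of those offered (0.6 × u) | Factor 1/u |
|---|---|---|---|---|---|
| 30% | 100% | 30% | 60% | 18% | 3.33 |
| 50% | 100% | 50% | 60% | 30% | 2.00 |
| 70% | 100% | 70% | 60% | 42% | 1.43 |
| 90% | 100% | 90% | 60% | 54% | 1.11 |

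**4. Is uptake available elsewhere in the SAP?**

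Partly. Section 7.4 gives the number offered or eligible by site, Table 11 gives raw counts at each threshold, and Table 12 gives a percentage attending at least once beside the number assigned to a group. A reader could divide one by another. However, being assigned to a group may be narrower than being offered the programme, and no percentage with all those offered as its base is explicitly planned at any threshold.

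**The case against.** The best defence is that the denominator in 7.4 is stated openly and is a legitimate measure of retention. It stands in a list that also reports the number offered or eligible, and Table 12 carries an uptake percentage. The number of sessions per participant is summarised too, with no stated restriction to attenders. A reader might infer from the denominator alone that the plan overstates uptake. The documents do not support that: the retention figures are not presented as uptake, and the uptake counts are planned nearby.

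A reader might also infer that these summaries are the only evidence on non-receipt. That is not supported either. Section 1.2 assigns engagement, referral and fidelity to the process evaluation, which section 1 says is described elsewhere. Table 3 reports withdrawal from the intervention by period. The CONSORT diagram and Appendix C are figures not shown here and cannot be assumed silent on attendance.

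On 7.5.2, the question is introduced only as an example, the analysis is descriptive, and it feeds a separate evaluation.

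All of this limits the weight of the point. It does not remove two facts: one of the planned percentages is 100% by definition, and the variables fixed for the complier comparison exclude the quantity the comparison asks about. Nothing in Table 12 or the offered counts helps with the second.

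**Conclusion.** The point holds in a limited form.

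- **Section 7.5.2** cannot address its stated question: none of its four variables is a score. Its label for need is reversed against the SAP's own scale descriptions. This follows from the text and rests on no assumption.
- **Section 7.4** gives an uninformative figure at one or more sessions and retention among attenders at the other thresholds. The excess over the share of those offered is exactly 1/uptake. The range of 1.11 to 3.33 depends on assumed uptake of 90% to 30% and illustrates the definition; it does not estimate what happened in this trial.

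No effect estimate, confidence interval or p-value in the SAP depends on either matter. The consequence is confined to how adherence is described and how the ITT result is explained.

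**What to change.** 1. **Section 7.5.2:** add PHQ-9 and ASQ:SE-2 at the eligibility visit to the compared characteristics, using FU1 for IY-I and FU2 for IY-T. Because FU1 may use the 2-month or the 6-month ASQ:SE-2, whose Monitoring thresholds are 25 and 30, the ASQ:SE-2 score is best shown relative to the threshold of the version completed.
2. **Section 7.5.2:** reword the example question so that scores just over the threshold are no longer called the greatest need.
3. **Section 7.4 and Table 11:** add, for each programme, percentages among all participants eligible for and offered it, with non-attenders counted as zero sessions. Keep the attender-only percentages, labelled as retention among attenders.

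The cost is a few table rows and one corrected phrase. Table 1 shows that both scores are collected at FU1 and FU2, and the offered/eligible count is already planned, so no new data are needed.
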